14.2.1 Primary Objective – Cohort B: Derivation and Analysis of the Primary Estimand

The primary efficacy endpoint for Cohort B is the response in BILAG-based Composite Lupus Assessment (BICLA) at Week 24, where a participant is BICLA responder if the following criteria are met:

- 1. BILAG 2004 improvement (all A scores at Baseline improved to B/C/D, and all B scores improved to C or D at Week 24)* AND
- 2. No worsening in disease activity (no new BILAG 2004 A scores and ≤ 1 new B score at Week 24) compared to Baseline AND
- 3. No worsening of total CCI score at Week 24 from Baseline AND
- 4. No worsening of ≥ 0.3 points in PGA of SLE disease activity score compared to Baseline (PGA score expressed on a 0-3 scale)
- * Participants in Cohort B may be included in the FAS with only 1 BILAG B score for a domain. For those, BILAG 2004 improvement will only be assessed on this single domain.

CONFIDENTIAL INFORMATION

Descriptive Analysis:

The number and percentage of participants with observed BICLA response will be presented during the on-treatment period. The number and percentage of participants meeting each BICLA component criterion will be provided during the on-treatment period. Intercurrent events will also be summarized at each time point.

Inferential Analysis:

The global null hypothesis (H0) for the Cohort B primary objective is the hypothesis that there is no difference in mean BICLA response at Week 24 between study intervention groups. H0 will be tested against the alternative hypothesis H1 of at least one of the active dose levels is superior to placebo at 0.025 alpha level.

Cohort B has a dose-finding adaptive design comprised of 2 parts. First part data and second part data will be analyzed separately to obtain 2 test statistics. Part 1 statistic Z_1 and part 2 statistic Z_2 will then be combined to form a final statistic that will be used to test the global null hypothesis using a weighted inverse normal method (Lehmacher 1999) as follows:

$$Z = \omega_1 Z_1 + \omega_2 Z_2$$
, where $\omega_1 = \frac{\sqrt{60}}{\sqrt{340}}$ and $\omega_2 = \frac{\sqrt{280}}{\sqrt{340}}$

Statistical hypothesis of no difference between study intervention groups will be rejected if $Z \ge z(0.975)$, where z(0.975) is the 97.5%-quantile from the standard normal distribution.

Analysis of Part 1 data – Difference Enpatoran 100 mg BID vs Placebo:

A logistic regression of BICLA response at Week 24 on study intervention group, CCl at Screening (source: IWRS) as categorical variables and CCl score at Baseline as a continuous variable will be conducted.

Odds ratio together with its 95% CI and the corresponding Part 1 one-sided p-value p_1 will be provided. Z1 will then be computed as $\Phi^{-1}(1-p_1)$ where Φ is the cumulative standard normal distribution.

The predicted probabilities (with 95% CI) and the difference in predicted probabilities (with 95% CI) between enpatoran 100 mg BID and placebo will be also provided.

Analysis of Part 2 data – Stage 1: covariate adjustment

A generalized MCP-Mod approach similar to that described in section 14.1.1 (primary analysis of CLASI-A in Cohort A) will be used to analyze the BICLA response at Week 24 in Part 2 participants. The analysis will be adjusted for the stratification factors.

In the first stage, a logistic model will be fitted to data to obtain $\hat{\mu}$ the vector of covariate-adjusted mean estimates on the logit scale, as well as \hat{S} the associated covariance matrix.

Analysis of Part 2 data – Stage 2: MCP Step

The optimal contrasts corresponding to the candidate models will be computed as described in section 14.1.1 to get Part 2 p-value p_2 which is defined as the smallest observed p-value among all candidate models.

 Z_2 will then be computed as $\Phi^{-1}(1-p_2)$ where Φ is the cumulative standard normal distribution.

Analysis of Part 2 data – Stage 2: Mod step

Model selection will be performed as described in section 14.1.1.

Covariate-adjusted estimates of the response probability together with their 95% CI will be provided at each dose level. The treatment effect in Part 2 participants will be estimated providing the difference in

CONFIDENTIAL INFORMATION

61/125

predicted probabilities between each active dose and placebo (and their 95% CI). The adjusted estimates of the response probability and their 95% CI will also be graphed.

14.2.3 Sensitivity Analysis 2 of the Primary Estimand regarding the Imputation of Missing data

In the primary analysis described in Section 14.2.1, participants with no available BICLA assessment (after imputation at the item level for CCI , PGA and BILAG questionnaires) at Week 24 are considered as non-responders. In this sensitivity analysis, ignoring imputation at item level is done for CCI , PGA and BILAG questionnaires (see 9.11.2 and 9.11.3 respectively), multiple imputation will be performed on BICLA response.

Multiple imputation will be performed under the missingness assumption of MAR. This assumption seems to be realistic given that participants who prematurely discontinued the treatment are considered as non-responder.

To be consistent with the analysis of Part 1 and Part 2 data separately, multiple imputation will also be conducted on the two parts separately.

Each missing component of BICLA response from Week 16 until Week 24 will be imputed. After all components are imputed, BICLA response at Week 24 will be derived in each imputed dataset. A total of 1000 imputed datasets will be produced. The following seed will be used for all imputation models: 1309201521.

Due to the small sample size in Part 1, 4 separate models will be run to impute each BICLA component as described below.

Imputation model for BILAG 2004 improvement (Yes/No) component will include the following variable:

• study intervention group, CCl at at Screening, baseline hybrid SELENA-SLEDAI score (continuous), BILAG 2004 improvement (Yes/No) at Week 16, Week 20, Week 24

Imputation model for "No worsening in disease activity from Baseline defined as no new BILAG 2004 A scores and ≤ 1 new B score" (Yes/No) component will include the following variable:

• study intervention group, CCl at Screening, baseline CCl score (continuous), No worsening in disease activity from Baseline (Yes/No) at Week 16, Week 20, Week 24

Imputation model for CCI	total score related component will include the following
variable:	•

• study intervention group, CCI at Screening, CCI score (continuous) at Baseline, Week 16, Week 20, Week 24

Imputation model for PGA related component will include the following variable:

• study intervention group, CCl at Screening, CCl score (continuous) at Baseline, PGA at Baseline, Week 16, Week 20, Week 24

First, for each of these imputation models, intermittent missing data will be imputed using MCMC (see Section 14.1.1). Subsequently, remaining missing values will be imputed under the assumption of monotone missing data patterns. For continuous variables, the monotone regression method will be used. For binary endpoints related to BILAG questionnaire, previously imputed missing data further to MCMC method will be rounded to the closest integer 0 or 1. Then, the monotone logistic regression will be used to impute remaining missing values.

BICLA response for Part 2 participants will be imputed from a single imputation model including the following variables:

- study intervention group, region, CCl at Screening
- CCl score (continuous) at Baseline, Week 16, Week 20, Week 24
- PGA at Baseline, Week 16, Week 20, Week 24
- BILAG 2004 improvement (Yes/No) at Week 16, Week 20, Week 24
- no worsening in disease activity from Baseline (Yes/No) at Week 16, Week 20, Week 24

As explained above, intermittent missing data will be first imputed using MCMC SAS statement to get a monotone pattern. Then, remaining missing data will be imputed using monotone regression or logistic method depending on the type of variables.

BICLA response will be derived in these 1000 imputed datasets.

For Part 1, the logistic model described in Section 14.2.1 will be run on each imputed dataset. The set of 1000 odds ratios and p-values obtained will be combined according to Rubin's rules and used to get Z1.

For Part 2, the logistic model described in Section 14.2.1 will be run on each imputed dataset. The vector of covariate-adjusted means $\hat{\mu}_i$ and the corresponding covariance matrix \hat{S}_i will be estimated from each fitted logistic model. The set of 1000 estimates obtained this way will then be combined according to Rubin's rules into a point estimate $(\hat{\mu}, \hat{S})$, the vector of covariate-adjusted mean estimates on the logit scale and the associated covariance matrix. The rest of the analysis will follow the primary analysis.

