6.3 Measures to Minimize Bias: Study Intervention Assignment and Blinding

6.3.1 Study Intervention Assignment

After confirmation of participant eligibility, study participants in each cohort will be centrally allocated to study intervention using an IVRS/IWRS and per a computer-generated randomization list:

• In Cohort A, the randomization ratio will be 1:1:1:1 ratio (enpatoran 25 mg twice per day: enpatoran 50 mg twice per day: enpatoran 100 mg twice per day: placebo) and the number of study participants randomly assigned to study intervention will be approximately 100.

- In Cohort B, the Part 1 participants will be assigned with a 2:1 ratio (enpatoran 100 mg twice per day: placebo). Part 2 participants will be assigned with a 1:1:1:1 ratio (enpatoran 25 mg twice per day: enpatoran 50 mg twice per day: enpatoran 100 mg twice per day: placebo. Part 2 dose levels and randomization ratio might be adapted after Cohort B IA.
- The IVRS/IWRS will be used to assign unique participant numbers, allocate participants to study intervention group at the Randomization Visit in DBPC treatment period, and allocate study intervention to participants at each study intervention visit.

Before the study is initiated, the telephone number and call-in directions for the IVRS and/or the log in information and directions for the IWRS will be provided to each site. The site will contact the IVRS/IWRS prior to starting study intervention administration for each participant.

Participants in Cohort A will be stratified by the following factors:

- Region (3 levels: North America and Western Europe vs Asia vs Central/South America and rest of the world),
- Disease diagnosis at Screening (2 levels: CLE [SCLE and/or DLE] vs SLE).

Participants in Cohort B will be stratified by the following factors (not all stratification factors might be used after Cohort B IA, as will be specified in the Interim Analysis Plan):

• Region (3 levels: North America and Western Europe vs Asia vs Central/South America and rest of the world),

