9.1 Statistical Hypotheses

Each cohort has its own primary objective and the respective null hypothesis will be tested with a 1-sided alpha of 2.5% separately.

Participants with CLE (active SCLE and/or DLE) or SLE with predominantly active rash (Cohort A)

The global null hypothesis for the Cohort A primary objective is the hypothesis that there is no dose-effect, which can also be stated as the hypothesis that the primary endpoint means across the study arms are equal.

The global null hypothesis is:

H0: μ(1) = μ(2) = μ(3) = μ(4) Hypothesis of no difference between study arms
 with μ(k) standing for the mean percent change from Baseline in CLASI-A at Week 16 in the study arm k, k = 1 to 4, with: 1 = Placebo only, 2 = enpatoran 25 mg twice per day, 3 = enpatoran 50 mg twice per day and 4 = enpatoran 100 mg twice per day. And μ is the vector of μ(k), k = 1 to 4.

H0 is tested against the alternative hypothesis (H1) is that at least one of $\mu(2)$, $\mu(3)$ and $\mu(4)$ is $< \mu(1)$.

The global null hypothesis can be rejected, if at least one of the following contrast tests can be rejected. An optimal contrast is defined for each candidate model M(m), m=1 to 5 as detailed in Section 8.2, is c(m)'. For each candidate model, the null hypothesis H0(m): c(m)' $\mu=0$ is tested against H1(m): c(m)' $\mu<0$.

The model M that fits the data best (e.g., smallest AIC statistic) will be chosen for dose-estimation and to further compare each enpatoran study arm to placebo: for each k = 2 to 4, the null hypothesis H0'(M, k): $\mu(1) = \mu(k)$ will tested versus H1'(M, k): $\mu(k) < \mu(1k)$

Participants with active SLE (Cohort B)

The global null hypothesis for the Cohort B primary objective is the hypothesis that there is no dose-effect, which can also be stated as the hypothesis that the primary endpoint means across the study arms are equal.

The global null hypothesis is:

```
H0: \mu(1) = \mu(k) \ \forall k \ge 2 Hypothesis of no difference between study arms
```

with $\mu(k)$ standing for BICLA response rate at Week 24 in the study arm k, with: 1 = placebo only, k = enpatoran dose k. And μ is the vector of $\mu(k)$.

H0 is tested against the alternative hypothesis (H1) is that at least one of $\mu(k) > \mu(1)$, $k \ge 2$.

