- Cohort B Part 1: 60 participants in a 2:1 ratio (enpatoran 100 mg twice per day: placebo).
- Cohort B Part 2 (up to 372 participants):
 - Up to 280 participants in a 1:1:1:1 ratio over 4 arms (placebo, enpatoran 25 mg twice per day, enpatoran 50 mg twice per day and enpatoran 100 mg twice per day).
 - In case of dose adaptation, up to 92 additional participants may be randomized and the randomization ratio may also be adapted (as will be specified in the Interim Analysis Plan).

CCI	

CCI	

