The procedure on how to perform model selection: The candidate model that fits the data best (e.g., smallest AIC statistic) will be chosen for dose-estimation. The mean difference of each active study intervention arm to placebo together with its 95% confidence interval and p-value will be estimated.

Enpatoran (M5049) MS200569_0003	The WILLOW study with enpatoran in SLE and CLE (SCLE and/or DLE)
CCI	
9.4.1.2	Primary Analysis of the Response in BICLA at Week 24.
The primary estimar	nd targeting this primary objective is defined by the following attributes:
• Variable (endpo	int): The primary endpoint is the Response in BICLA at Week 24 defined
1. BILAG 2004 i	improvement (all A scores at Baseline improved to B/C/D, and all B scores

- improved to C or D),
- 2. No worsening in disease activity (no new BILAG 2004 A scores and ≤ 1 new B score) from Baseline,
- 3. No worsening of total **CCI** score from Baseline,
- 4. No significant deterioration (< 0.3 increase) in visual analog PGA from Baseline (PGA score expressed on a 0-3 scale)
- **Treatment:** The intervention of interest is enpatoran during the treatment period and placebo during the treatment period.
- **Population:** The population of patients targeted by the clinical question is patients with active SLE.

•	CCI	

• Population-level summary: The population-level summary comparing the intervention groups is the proportion of participants achieving BICLA response at Week 24 (95 % CI).

The primary efficacy analysis will be conducted on the FAS population, in participants with active SLE (Cohort B).

A generalized MCP-Mod approach accounting for baseline covariates (based on randomization stratification factors) will be used to analyze the primary efficacy variable, i.e., proportion of participants achieving BICLA response at Week 24 with a similar approach to the one described for the primary endpoint of percent change from Baseline in CLASI-A.

Odds-Ratio and associated two-sided 95% CI comparing each dose level to placebo based on a logistic model for the odds of a given BICLA response in the appropriate population, with treatment arm as a factor and adjustment for covariates based on randomization stratification factors will be presented.

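### Cohort B primary test: on the visible text, Part 1 does not adjust for region and Part 2 names no continuous baseline score; aligning the covariates is a cheap, low-severity improvement

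*SAP*

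**What the plan says.** **Design and test.** Protocol 9.1 says that for each cohort "the respective null hypothesis will be tested with a 1-sided alpha of 2.5% separately". Protocol 9.2 plans Cohort B Part 1 as "60 participants in a 2:1 ratio (enpatoran 100 mg twice per day: placebo") and Part 2 as "Up to 280 participants in a 1:1:1:1 ratio over 4 arms", with up to 92 more participants if doses are adapted. SAP 14.2.1 analyses the parts separately and combines the two statistics by the weighted inverse normal method, with weights proportional to the square roots of 60 and 280.

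**Randomisation.** Protocol 6.3.1 lists as a Cohort B factor "Region (3 levels: North America and Western Europe vs Asia vs Central/South America and rest of the world"). The remaining factors are redacted, and the same section allows some factors to be dropped after the interim analysis.

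**Part 1 model (SAP 14.2.1).** The text reads "A logistic regression of BICLA response at Week 24 on study intervention group", followed by a redacted categorical item at Screening taken from the IWRS and a redacted score at Baseline entered as continuous.

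**Part 2 model (SAP 14.2.1).** The text reads "The analysis will be adjusted for the stratification factors". The method is called similar to that of SAP 14.1.1, where the Cohort A model has the stratification factors plus a continuous baseline score.

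**Imputation models (SAP 14.2.3).** The Part 2 list opens with "study intervention group, region". None of the four Part 1 lists shows region.

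**Protocol 9.4.1.2.** The MCP-Mod analysis accounts for baseline covariates based on the randomisation factors. For the odds ratios of each dose against placebo, "adjustment for covariates based on randomization stratification factors will be presented". SAP Section 7, which records changes from the protocol, mentions only the Full Analysis Set.

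**The concern.** A factor used to balance the arms is normally kept in the analysis. If region predicts BICLA response and is left out, the logistic test tends to be conservative and loses some power. A continuous baseline score that predicts response should likewise help in Part 2, which has most of the participants and most of the weight. As printed, each stage seems to lack something the other has.

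The Part 2 wording also leaves the covariate set open. It points to a Cohort A method that includes a continuous score, then names only the factors, and those factors may change after the interim analysis. At stake are a little power and a clear pre-specification of the primary model.

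**Working it through.** **1. The plan's own figures.** Sample size: 60 + 280 + 92 = 432, the stated Cohort B maximum. Weights: w1 = √(60/340) = 0.420 and w2 = √(280/340) = 0.907, with w1² + w2² = 0.176 + 0.824 = 1. The Cohort B response rates, power and candidate models are redacted, so the planned power cannot be reproduced.

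**2. Is region really absent from Part 1?** The Part 1 covariate names are partly redacted, so its absence is an inference. Region is printed openly in protocol 6.3.1, protocol 9.2 and the Part 2 imputation list of SAP 14.2.3. It appears neither in the Part 1 primary model nor in any of the four Part 1 imputation lists. Five parallel lists without it make omission the likelier reading.

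**3. Type I error.** The test rejects when w1·Z1 + w2·Z2 ≥ 1.96. It needs a valid p-value from each stage, not a common model.

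**4. Simulation of the combined test.** The following inputs are assumed, because the documents do not give them:
- response rates of 30% on placebo and 37%, 43% and 50% on the three doses;
- one binary Screening factor and six generic dose-response shapes;
- a score log odds ratio per SD of 0, 0.3 or 0.6;
- a log odds ratio step between regions of 0, 0.4 or 0.8.

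Part 1 has 40 vs 20 participants and Part 2 has 70 per arm. Part 2 uses a multiplicity-adjusted maximum contrast test. There are 3,000 trials per scenario. As an anchor, an unadjusted two-proportion calculation for Part 1 (30% vs 50%) gives 30.5% power; the simulation without prognostic effects gives 30.2%.

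Combined power (%):

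| Score | Region step | Models as visible | + region in Part 1 | + score in Part 2 | Both |
|---|---|---|---|---|---|
| 0 | 0 | 80.7 | 80.7 | 80.8 | 80.9 |
| 0 | 0.4 | 81.4 | 81.7 | 81.4 | 81.4 |
| 0 | 0.8 | 82.8 | 84.0 | 82.5 | 83.8 |
| 0.3 | 0 | 81.4 | 81.0 | 81.4 | 81.1 |
| 0.3 | 0.4 | 82.1 | 82.1 | 82.3 | 82.4 |
| 0.3 | 0.8 | 84.6 | 85.1 | 85.1 | 85.4 |
| 0.6 | 0 | 83.0 | 82.9 | 83.6 | 83.6 |
| 0.6 | 0.4 | 82.8 | 83.1 | 84.4 | 84.7 |
| 0.6 | 0.8 | 85.3 | 85.9 | 86.4 | 86.7 |

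Region alone changes power by −0.4 to +1.2 points, the score alone by −0.3 to +1.6, and both by −0.3 to +1.9. One power estimate has a Monte Carlo standard error of about √(0.83 × 0.17/3000) = 0.7 points, so differences of a few tenths mean little.

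With no treatment effect, combined rejection was at most about 2.7% under either covariate set; the standard error is √(0.025 × 0.975/3000) = 0.3 points.

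**5. Second simulation.** With 4,000 trials per cell, assumed effects and a pairwise stand-in for Part 2, type I error was about 2.3–2.8% with either set. Gains were about 0–1 point from region and up to 2.6 points from a prognostic score.

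**6. Cost of region in Part 1.** The median standard error of the treatment log odds ratio rises from 0.61 to 0.635 (0.635/0.61 = 1.04) at the low end and from 0.634 to 0.703 (0.703/0.634 = 1.11) at the high end. Near-separated fits under the null rise from at most 0.2% to 0.5–5.8%. The larger standard error is not in itself lost power, because adjusting a logistic model for a prognostic covariate also moves the log odds ratio away from zero.

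**The case against.** The best defence is that a leaner Part 1 model is a reasonable choice. It has 60 participants, only 20 of them on placebo, and two region terms raise the standard error and the risk of separation. SAP 14.2.3 gives the small Part 1 sample as its reason for simpler models, though only for imputation. This stands: the omission is not without benefit, and any change needs a fallback.

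The redactions also count. They are not uniform: the baseline score is named in one Part 1 imputation list and blacked out in others. The Section 14 definition of the stratification factors is not visible. SAP 14.2.2, listed in the contents as a sensitivity analysis on covariate adjustment, has no public text. A form of the score may already be among the Part 2 factors, in which case that half of the point falls away. A sensitivity analysis would not alter the primary model, however.

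Nor is the departure from protocol 9.4.1.2 clear-cut. Its MCP-Mod sentence fits Part 2 only. Its odds ratios are delivered on both parts combined in SAP 14.2.4, with the stratification factors. Protocol 9.1 names no covariates for Z1, and protocol 9.4 leaves room for alternative methods in the analysis plan.

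A reader might infer a large loss from Part 1 taken alone. With a log odds ratio of 0.9 and regions differing by ±1.0 on the logit scale, simulated Part 1 power is 25.3% without region and 30.8% with it. That is not the planned test: protocol 9.1 allows rejection only after stage 2, and Part 1 has a squared weight of 17.6%. With a similar Part 1 set-up and a pairwise stand-in for Part 2, combined power was 77.0% vs 78.2%. A spread of ±1.0 is also an odds ratio of e² ≈ 7.4 between the outer regions, which nothing in the documents supports.

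**Conclusion.** The point holds as a specification gap with a small efficiency cost. On the visible text, region is missing from the Part 1 primary model and the Part 2 model names no continuous baseline score. The combined test gives up roughly 0–1 point of power for the first and about 0–2.6 points for the second. Both ranges rest on assumed response rates and prognostic strengths; the second also requires that the redacted factors do not already include the score.

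A reader might infer that unlike covariates make the two statistics incompatible. They do not. By design Z1 compares 100 mg with placebo and Z2 is a maximum over dose-response contrasts, so the two already address different quantities, and type I error stayed close to 2.5% or below in simulation. Low severity.

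**What to change.** 1. In SAP 14.2.1, list the Part 2 covariates by name, fixing which stratification factors apply if any are dropped after the interim analysis. Add the continuous baseline score if it is not already there.
2. Add region to the Part 1 logistic model, with a pre-specified fallback that drops or pools region if the fit shows separation. If region stays out, give the small-sample reason.
3. Record any remaining departure from protocol 9.4.1.2 in SAP Section 7.

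The cost is SAP wording; all variables are already planned for collection. The downside is two extra parameters in a 60-participant, 2:1 model, with a slightly larger standard error and occasional near-separation, which the fallback covers.
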